5.6.2 Data security

Hard copies of data and study documentation will be kept in locked offices, and long term storage will be in locked cupboards in a locked repository.

Electronic copies of data will be saved in password-protected files. All data will be backed up daily by the MLW Data Office, with offsite back up once weekly. Backup data will be stored in a locked filing cabinet away from the office by the PI.

5.6.3 Quality assurance

Data will be checked for internal inconsistencies during verification and following data entry. Quality assurance protocols will be developed for each stage of the study, detailed as SOPs.

PSI supervisors will carry out periodic spot-checks on CBDAs, with visit at home of recent HIVST participants.

ART clinic data will be extracted by PSI supervisors. MLW data team will check data and raise any queries, and will also visit each ART clinic quarterly.

5.6.4 Outcome evaluation

For the comparison of **coverage of recent** / **ever HIV testing**, outcomes will be evaluated through household surveys as detailed above.

For evaluation of **ART initiations within study area villages**, maps showing study area boundaries and names of participating villages will be produced and displayed in HCT and ART clinics. ART register completion will be adjusted in collaboration with MoH to allow previous HIVST / home-initiation episodes to be documented in the "Comments" column.

Clinic staff will be asked to ensure that all clients are asked directly if they are attending following HIVST results and that the village of residence is clearly recorded in the ART register. The self-referral cards, which are presented by the participants to the clinic, will contain spaces for ART clinic staff to log confirmatory results, the national ART number for clients entering HIV care, and any other relevant referrals (e.g., VMMC).

PSI CBDA supervisors will extract these data on a monthly basis from each of the 20 ART clinics included in the study. Retrospective data extraction will also be used to provide an indication of pre-intervention ART initiations from the 20 study clinics.

In **Home-Initiation villages**, where participants have the option of requesting home initiation of care, PSI CBDA supervisors will fill out HIV care registration cards and maintain a logbook allowing cross-reference by ART number with the local ART clinic. Total numbers of clients confiding positive HIVST results will be recorded by all CBDAs in post-test logbook recording disclosure and other referral events without name.

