1.2 Research description

The HIV STAR Malawi General Population (HIV STAR Malawi GP) study consists of a cluster-randomised trial investigating the effects of introducing HIVST to the remit of volunteers providing reproductive health services to villages in up to 5 Southern Region Districts. This research protocol is nested into the UNITAID/PSI HIV Self-Testing Africa (HIV STAR) project, which is funded to provide 34,068 episodes of HIVST in Malawi during 2016/17 with potential extension to 2018/19.

The trial population will be the catchment population (~62,500 adults) of 20 Rural Primary health clinics that have a) ART services and b) support the activities of reproductive health community-based distribution agents (CBDAs). CBDAs are lay volunteers trained and supervised by PSI to socially market reproductive health products in the rural areas.

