2.3 UNITAID/PSI HIV STAR project

The UNITAID/PSI HIV STAR project will conduct HIVST implementation research to generate the evidence base required for WHO guidelines in Malawi, Zambia and Zimbabwe. The project has a dual focus on marginalised sections of the general population (defined by poor coverage of HTC under current strategies) and key populations (i.e., FSWs, MSM).

Collaborators include WHO, Population Services International (PSI), London School of Hygiene and Tropical Medicine (LSHTM), Liverpool School of Tropical Medicine (LSTM), and University College London (UCL).

PSI is responsible for HIVST implementation, while LSHTM, in conjunction with local partners (the Malawi-Liverpool-Wellcome Trust Clinical Research Programme (MLW) in Malawi) is responsible for implementation research. WHO will lead the development of policy and regulatory guidelines around HIVST.

The funding body for the UNITAID/PSI HIV STAR project is UNITAID, a United Nations organisation housed within WHO that supports the development and optimisation of robust, high-quality and low-cost products specifically intended to meet the diagnostic and pharmaceutical needs of HIV, tuberculosis (TB) and malaria programmes in low-resource countries.

Figure 1. HIV STAR Project Organogram

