4.3.2 Secondary Outcome for main HIVST versus SOC CBDA intervention

The secondary outcome is: Comparison between randomisation arms of ART initiation rates for adult (16 yrs or older) cluster residents, during months 1 to 12 of intervention.

This analysis will be based on data extraction from routine ART clinic records. Residential address will be used to identify all new initiations among adults (16 years or older) living within the the wider CBDA catchment area relating to that clinic.

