5.3 Randomisation and investigator blinding

Following baseline enumeration, ART clinic-evaluation village pairs will be randomly allocated to the intervention or control arm at a public ceremony using constrained randomisation.

Balls or discs numbered 1-N (where N represents the number of possible randomisation combinations) will be selected from an opaque bag by a stakeholder representative. The selected number will correspond to a pre-specified combination of clinics in Arms A and B.

A second opaque bag containing 2 balls – one for HIVST and one for SOC – will then be used to allocate the arm to the selected combination in a second drawing process. It will not be possible to blind participants, community workers, or their supervisors to the cluster intervention allocation, but all specimens and forms and data analysis conducted by laboratory, data, and health facility staff will be managed without reference to the intervention arm.

Outcome data will not be analysed by intervention arm until the final data analysis after completion of the trial, with the exception of data analysis by an independent statistician for presentation to the Data Safety Monitoring Board.

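### ART initiations, counted by residential address, are extracted by unblinded staff of the implementing organisation, and no masked coding of residence is described

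*Protocol*

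**What the plan says.** ART initiation is the secondary outcome of the main comparison (Protocol 4.3.2) and of the second-stage randomisation to home assessment or HIVST only (4.3.3). For the main comparison, "Residential address will be used to identify all new initiations among adults" living in the wider CBDA catchment of the clinic.

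On who collects the data, section 5.6.4 says "PSI CBDA supervisors will extract these data on a monthly basis from each of the 20 ART clinics included in the study", and section 5.6.3 says "ART clinic data will be extracted by PSI supervisors". On the position of these staff, section 2.3 says "PSI is responsible for HIVST implementation", and section 1.2 says "CBDAs are lay volunteers trained and supervised by PSI". In home-initiation villages, "PSI CBDA supervisors will fill out HIV care registration cards and maintain a logbook" (5.6.4).

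On the source records, section 5.6.4 has the village of residence written in the ART register by clinic staff. It also has earlier HIVST or home-initiation episodes noted in the register's Comments column, and adds: "Clinic staff will be asked to ensure that all clients are asked directly if they are attending following HIVST results". Self-referral cards are handed in at the clinic as well.

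On masking, section 5.3 accepts that the supervisors of the community workers cannot be blinded. It then says that "all specimens and forms and data analysis conducted by laboratory, data, and health facility staff will be managed without reference to the intervention arm".

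**The concern.** Whether an initiation counts turns on how an address is read. Some addresses in a rural register will be vague or shared between places. The people named as extractors know the arm: the clinic is the unit of randomisation, and they supervise the volunteers. The records also give client-level cues that hardly exist in standard-of-care (SOC) clinics, such as an HIVST note, a self-referral card or a home-initiation log entry. A client with such a cue is easier to place inside the catchment when the address is unclear.

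If that happened, the count would rise in the HIVST arm with no change in the number of people starting ART at the clinic. Increased demand for ART is one of the protocol's main research questions, and this is the only secondary outcome of the main comparison. The second-stage comparison is the more exposed of the two: village of residence itself sets the arm there, and the supervisors complete registration cards only in the home-initiation villages.

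**Working it through.** The protocol gives no initiation rate, no attribution rate and no figure on this point, so there is nothing of its own to reproduce. The check has three steps.

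**1. What each stated safeguard reaches**

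| Safeguard | Section | Fixes the boundary? | Masks or re-codes residence? |
|---|---|---|---|
| Evaluation areas defined before randomisation | 4.1 | Yes | No |
| Maps and village names displayed in clinics | 5.6.4 | Helps recording | No |
| Clinic staff write the village in the register | 5.6.4 | Helps recording | No |
| MLW data checks, queries and quarterly clinic visits | 5.6.3 | No | Not described |
| Supervisory visits and data quality audits | 5.7.1, 10.2 | No | Not described |
| Adjustment for pre-intervention initiation rates | 5.8.4 | No | No; the HIVST cues do not exist before the intervention |

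These make recording better in both arms. None supplies a rule for unclear addresses, and none is described as masked or as an independent coding of residence.

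**2. Size of the bias**

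Let s1 and s0 be the shares of true catchment initiations that are counted in the HIVST and SOC arms. Then

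observed rate ratio = true rate ratio × s1/s0.

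With a true ratio of 1 and assumed shares:

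- 100% and 95%: 1.00/0.95 = 1.05
- 90% and 85%: 0.90/0.85 = 1.06
- 95% and 85%: 0.95/0.85 = 1.12
- 90% and 80%: 0.90/0.80 = 1.125
- 95% and 75%: 0.95/0.75 = 1.27
- any equal shares: 1.00

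Only a difference between arms matters. Incomplete capture that is the same in both arms leaves the ratio unbiased.

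**3. Effect on the planned test**

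From the protocol: 10 clusters per arm (7.2); a t test on log cluster rates with 18 degrees of freedom (5.8.5); about 62,500 adults in 20 catchments (1.2), so 62,500/20 = 3,125 per cluster. Assumed: 3 to 10 counted initiations per 1,000 adults in SOC clusters over the 12 months, and a between-cluster coefficient of variation k of 0.15 to 0.25. Section 7.2 uses 0.25, but for HIV testing.

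With E = 3,125 × rate/1,000 expected events per SOC cluster and RR the spurious ratio,

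SE = √[(k² + 1/E)/10 + (k² + 1/(E × RR))/10].

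The false-positive rate is the two-sided 5% rejection probability of a noncentral t with 18 degrees of freedom and noncentrality ln(RR)/SE.

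Example, with k = 0.25, rate 5 per 1,000 and 95% against 85%: E = 15.6; SE = √[(0.0625 + 0.0640)/10 + (0.0625 + 0.0573)/10] = 0.157; ln(1.118) = 0.111; noncentrality 0.111/0.157 = 0.71; false-positive rate 10.3%.

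| Assumed capture, HIVST against SOC | Spurious ratio | False-positive rate over the assumed range (nominal 5%) |
|---|---|---|
| 100% against 95% | 1.05 | 6% to 8% |
| 95% against 85% | 1.12 | 9% to 18% |
| 95% against 75% | 1.27 | 24% to 60% |

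These rows show what given gaps would do. They are not evidence that any such gap exists.

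**The case against.** Several stronger readings are tempting, and the protocol does not support them.

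- *A reader might infer that section 5.3 is contradicted.* For these extractors it is not. The masking statement names laboratory, data and health facility staff, and the same sentence first excepts the community workers' supervisors. What does stand is narrower. A reader of 5.3 could believe that outcome handling is masked throughout, while the ART data come from people outside the masked group. Facility staff, who are inside it, are asked to find out about and record prior HIVST.
- *A reader might infer that the supervisors decide who lives in the catchment.* The protocol does not say so. Clinic staff write the village, and section 4.3.2 names no coder. Full extraction followed by coding in the data office, which 5.3 places under masked handling, fits the text equally well. The coder could also be named in an SOP, since 5.6.3 promises one for each stage. But the alternative is not stated either, and the protocol does fix who extracts.
- *A reader might infer that the extractors also replace kits and deliver home care.* Section 5.4.1 gives kit replacement to the PHC clinic supervisors, and the home assessment to an ART-trained nurse whose visit the CBDA arranges. The PSI supervisors' stated part in home initiation is the registration cards and the logbook. The conflict of role rests on that and on PSI's position as implementer.

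It can also be said that one group extracts at all 20 clinics, which favours consistency, and that allocation is drawn in public by clinic, so anyone coding village names may infer the arm. Both are true. The first does not remove the client-level cues. The second means that masking can only be partial.

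**Conclusion.** The point holds as a risk of differential attribution in a secondary outcome. An unblinded group from the implementing organisation extracts a residence-defined count from records that carry cues found essentially in one arm. The protocol names no one to decide catchment membership, and describes no masked or independent coding.

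It does not show that bias occurs, and it gives no basis for its size. The ratios of 1.05 to 1.27 rest wholly on assumed capture shares, and the false-positive rates also on assumed initiation rates and k. The direction is a presumption as well, though the cues point towards the HIVST arm. The primary outcome comes from household surveys and is not touched. The change is worth making because it is cheap, not because the secondary outcome is shown to be unsound.

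**What to change.** 1. Extract every new adult ART initiation at each of the 20 clinics, with the recorded address copied verbatim. The same supervisors can do this.
2. Have the MLW data team code residence against the village list fixed before randomisation, using a written rule for unclear addresses. The coders work without the Comments column, the self-referral cards, the home-initiation log and the allocation list. Base the outcome on this coding for both randomisations.
3. Report all-address adult initiations per clinic as a sensitivity analysis that does not depend on residence coding. It serves the main comparison only, since residence sets the arm in the second stage. It will also dilute a true effect, because it includes clients from outside the catchment.
4. Amend section 5.3 to say that ART outcome extraction is unmasked and that health facility staff are asked to record prior HIVST.

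The cost is an amendment to the extraction and coding SOPs and more register lines to transcribe and code, with no new staff. Masking stays partial because clinic and village names may reveal the arm. The gain comes from removing the client-level cues and applying one rule to both arms. How clinic staff record the village is unchanged.

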5.7 Data management

5.7.1 Quantitative data management

Quantitative data will be captured using electronic devices (Tablets) or onto Optical Character Recognition forms, and entered into a dedicated database (Microsoft Access). Incoming electronic data will be checked on a daily basis for errors, with supplemental training provided to field staff if required. In the case of external manual data, MLW-LSHTM will provide training on data collection and assess quality and accuracy through quarterly (initially monthly) supervisory visits.

All data will be cleaned and analysed using Stata software (Stata Corporation, College Station, Texas, USA). All participants will be assigned a study ID number. Participant names will not be linked except through paper-based recruitment logs, which will be stored in locked cupboards and not entered into electronic form.

5.7.2 Qualitative data management

Qualitative data will be recorded in two forms – observational notes and digital audio recordings – and cross-referenced for accuracy. A backup copy of the audio file will be saved on RedCAP, the MLW data management programme, while another copy will be sent to the transcription and translation team. The audio file will be transcribed verbatim into written chiChewa. Transcriptions and notes will then be translated into English. All data will then be transferred to a qualitative data analysis software package, NVIVO 10 (QSR, Melbourne, Australia) and filed according to document type. Coded data will be transferred to a Microsoft Excel spreadsheet for broader thematic analysis.

5.8 Data analysis

Standard approaches to analysis CRT data will be used. Sample size calculations are detailed in the Statistical Considerations section.

5.8.1 Description of the HIVST and SOC arms in the baseline survey

The characteristics of participants recruited into the baseline survey will be described by arm (HIVST and SOC). Cluster-level factors will be summarised at baseline using the mean, median and range, by intervention arm, based on data from the facility assessment, conducted at baseline.

5.8.2 Description of the HIVST and SOC arms in the follow-up survey

The characteristics of participants recruited into the follow-up survey, by arm (HIVST and SOC) will be described. All characteristics will be compared by arm of the trial to assess for comparability. Any variables for which there is a substantial imbalance will be noted so that final analysis can take this into account. This assessment will not be based on the results of hypothesis tests, and p-values will not be shown.

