5.2.2 Baseline household surveys

All households in the evaluation villages will be visited for enumeration and invited to participate in the baseline household survey (PS401A). Village boundaries will be defined by obtained GPS coordinates.

An appointment will be made to visit the head of household or authorised individual to explain the study. All adults and older adolescents will be asked for verbal consent to participate, with verbal consent from guardians required in the case of adolescents.

As part of the baseline household survey, a household-level questionnaire of household size, age and gender composition, and socioeconomic indicators will be administered. Each adult household member will then be asked for verbal consent to participate in a brief individual questionnaire on demographic characteristics and experience with HIV testing and care.

A random selection of participants will then also be asked for written consent to complete an extended individual questionnaire on sexual behaviour, stigma, and health service utilisation, including costs. A discrete choice module will investigate user preferences for HIV delivery and linkage to care.

One in 4 household survey participants will be randomly allocated to a longer questionnaire (PS401B/PS402A), includes an approach to establishing user preferences by asking participants to make a series of trade-off choices (discrete choice experiment: DCE). Written or witnessed informed consent (or assent with guardian consent in the case of adolescents) will be obtained beforehand. Selection will be determined based on a random number generated by the electronic survey device at the time of the household survey (Choko, et al. 2015).

A post-intervention survey will be conducted with the same evaluation villages 12 months after the start of HIVST services. The post-intervention survey will consist of the household and brief individual questionnaires as well as an additional section on self-testing.

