5.8.4 Outcomes

Overall numbers of ART initiations per 1,000 total adult population will be calculated for each clinic during months 1 to 12, and will be compared between intervention and control arms after adjusted for any major imbalance between the trial arms in factors such as pre-intervention ART initiation rates.

The proportion of residents accepting HIV testing will be estimated both overall and within sex, age and village strata, using population denominators from the post-intervention household prevalence survey. Participant characteristics during different time periods of the study will also be compared.

Estimates of linkage into newly accessed care will be assessed using the referral completion rate. This will compare the number of participants who disclosed positive results to CBDAs during a specific period of time to the number of participants accessing confirmatory testing following HIVST over the same time period.

The number of new HIV-positive cases will be ascertained through re-reading of returned kits and participants sharing results with CBDAs.

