5.8.5 Methods

All statistical analyses will be based on methods used for CRTs with a small number of clusters (Campbell, et al. 2012). The analysis for the first randomisation is based on a total of 20 clusters.

Summary measures

For binary outcomes the overall risk, combining data across clusters, and means of clusterlevel risk will be reported by intervention arm. For quantitative outcomes, the overall mean and cluster-level means will be reported by intervention arm.

Unadjusted analysis

The analysis will give each cluster equal weight. The overall risk/mean for each cluster will be calculated.

A log transformation (where necessary) will be applied to the risk/rate/mean for each cluster. For binary outcomes where there are clusters with no events, one event will be added to all clusters so that the log transformation can be conducted. The mean and standard deviation of these log risks/rates/means will be used to obtain the geometric mean (GM) and associated 95% CI for each arm of the study.

The risk/mean ratio, 95% confidence interval and p-value is estimated using a t test and the log risks/rates/means by arm, based on 18 degrees of freedom.

Adjusted analysis

Factors for adjustment will be determined as stated above.

Depending on the outcome to be analysed, logistic/linear regression will be used to adjust for confounders at the individual level and cluster level, adopting a two-stage approach.

The regression model will include terms for the individual level adjustment factors, but not study arm. For each cluster the fitted model will be used to obtain the ratio of observed to expected (O/E) events, and a log transformation will be applied to this ratio, where appropriate. A t test of the log (O/E) by arm will be used to estimate the risk ratio, 95% CI and p-value. If adjustment for cluster level factors is considered necessary, this will be conducted at the second stage using linear regression of the log (O/E) on arm and cluster level factors, with appropriate adjustment for the degrees of freedom.

Stratified (subgroup) analyses

Stratified analyses (sub-group) for the primary outcome will be pre-specified before the end of data collection,

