7.2. CRT sample size calculations

This trial has one primary and one secondary outcome, with a number of other analyses to be specified in the Statistical Analysis Plan. The sample size considerations here relate to the main Primary Outcome (comparison between arms of recent HIV testing).

A survey sample of 250 to 500 adults per cluster will provide sufficient power for a two sample comparison of unmatched proportions for HTC coverage was performed across the intervention and control arms to determine the number of clusters per arm.

The cluster size is based on the typical size of a rural village (250-500 people) from previous experience in Malawi. Using 2010 DHS data, baseline rates for individuals tested in the last 12 months is estimated at 25% to 40%, with a 45% to 60% predicted effect size in the intervention arm compared to the control arm. Baseline coverage for individuals who have ever tested is estimated at 42% to 60% with predicted effect size 30%-45%.

Figures 10 and 11 contain a table of scenarios for each of the outlined assumptions. To detect a 50% increase in rate of people testing in the past 12 months and a 45% increase in the percentage of people who have ever tested in the intervention villages, there should be approximately 8 clusters per arm and approximately 4,000 participants total. This study will aim to reach 10 clusters per arm and 5,000 participants to provide contingency for a lower than anticipated effect size.

1-type l	Power	Baseline testing	Effect size	Interven- tion testing	Cluster size	k	Number of clusters	Total partici- pants
0.95	0.8	0.35	0.6	0.56	250	0.25	6.19	3094.21
0.95	0.8	0.3	0.6	0.48	250	0.25	6.30	3148.20
0.95	0.8	0.25	0.6	0.4	250	0.25	6.45	3223.78
0.95	0.8	0.35	0.55	0.5425	250	0.25	6.92	3460.38
0.95	0.8	0.3	0.55	0.465	250	0.25	7.05	3523.39
0.95	0.8	0.25	0.55	0.3875	250	0.25	7.22	3611.61
0.95	0.8	0.35	0.5	0.525	250	0.25	7.87	3933.04
0.95	0.8	0.3	0.5	0.45	250	0.25	8.02	4007.80
0.95	0.8	0.25	0.5	0.375	250	0.25	8.22	4112.45
0.95	0.8	0.35	0.45	0.5075	250	0.25	9.12	4560.03
0.95	0.8	0.3	0.45	0.435	250	0.25	9.30	4650.47
0.95	0.8	0.25	0.45	0.3625	250	0.25	9.55	4777.08

Figure 10. Sample size calculation – tested for HIV in last 12 months

Figure 11. Sample size calculation – ever tested for HIV

1-type l	Power	Baseline testing	Effect size	Interven- tion testing	Cluster size	k	Number of clusters	Total partici- pants
0.95	0.8	0.6	0.45	0.87	250	0.25	8.67	4333.93
0.95	0.8	0.5	0.45	0.725	250	0.25	8.79	4397.24

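### Adjustment factors for the primary outcome are to be chosen by imbalance in the post-intervention survey, while baseline testing coverage has no committed role

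*Protocol*

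**What the plan says.** Protocol section 5.8.2 describes respondents to the follow-up survey by arm and compares every characteristic, without hypothesis tests or p-values. It continues: "Any variables for which there is a substantial imbalance will be noted so that final analysis can take this into account". Under the adjusted analysis in section 5.8.5 the protocol says only "Factors for adjustment will be determined as stated above". For the primary outcome, nothing before that sentence gives any other selection rule. Section 5.8.1 is limited to describing the baseline data.

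The method in section 5.8.5 has two stages. Stage 1 is an individual-level regression without arm, giving observed/expected ratios by cluster. Stage 2 compares the log ratios between arms and may include cluster-level factors where that is thought necessary. No factor is named.

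On the baseline data, section 5.2.2 says "All households in the evaluation villages will be visited for enumeration and invited to participate in the baseline household survey", and each consenting adult is asked about HIV testing. Section 1.4 confirms that recent testing is asked at both surveys. The same villages are surveyed again at 12 months.

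For the secondary outcome, section 5.8.4 compares ART initiations "after adjusted for any major imbalance between the trial arms in factors such as pre-intervention ART initiation rates". Section 5.6.4 provides for retrospective extraction of pre-intervention initiations from the study clinics.

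Clusters are "randomly allocated to the intervention or control arm at a public ceremony using constrained randomisation" after baseline enumeration (section 5.3). The constraint factors are not listed.

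**The concern.** The rule has three weaknesses.

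- **Timing.** The variables are measured after 12 months of intervention. By section 5.2.2 the follow-up survey repeats the household and brief individual questionnaires, the latter covering experience of testing and care, and adds a section on self-testing. Section 5.8.2 excludes none of these. Adjusting for something self-testing has changed can remove part of the effect being estimated.
- **Discretion.** The choice is made with arm-level follow-up data in view, and what counts as substantial is undefined. Leaving out p-values does not remove that freedom. The adjusted estimate and its p-value depend on what is chosen.
- **Criterion.** Observed imbalance is a poor guide to what is worth adjusting for. With 20 clusters, between-cluster variation dominates the standard error, and a prognostic baseline value reduces it whether or not the arms happen to differ on it. The obvious candidate is each cluster's own baseline level of the primary outcome, which the trial already collects.

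The same criterion governs the secondary outcome: pre-intervention ART initiation rates are used only if there is major imbalance.

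**Working it through.** **1. The plan's own figure.** Inputs from section 7.2, Figure 10, the row "0.95 0.8 0.3 0.5 0.45 250 0.25 8.02 4007.80": two-sided alpha 0.05, power 0.80, p0 = 0.30, p1 = 0.45, m = 250, k = 0.25. The standard formula for an unmatched cluster trial is

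c = 1 + (z0.975 + z0.80)² × [p0(1−p0)/m + p1(1−p1)/m + k²(p0² + p1²)] / (p1 − p0)²

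= 1 + 7.849 × [0.00084 + 0.00099 + 0.01828] / 0.0225 = 1 + 7.02 = 8.02 clusters per arm.

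Total = 8.0156 × 2 × 250 = 4,007.8. This reproduces the table, as do all 12 rows of Figure 10, and agrees with the text: "there should be approximately 8 clusters per arm and approximately 4,000 participants total". The calculation assumes no baseline adjustment and is not in error. The planned size is larger: "This study will aim to reach 10 clusters per arm and 5,000 participants".

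**2. Share of variance between clusters.** On the log scale used in section 5.8.5, the variance of one cluster's log risk is about k² + (1−p)/(mp). In a control cluster at p = 0.30 this is 0.0625 + 0.70/75 = 0.0625 + 0.0093 = 0.0718. Between-cluster variation is 0.0625/0.0718 = 87% of it.

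**3. Effect of a baseline covariate.** Let r be the correlation between a cluster's baseline and follow-up log coverage. The protocol does not give it, so 0.3, 0.5 and 0.7 are assumptions. Adjustment multiplies the variance by 1 − r², that is by 0.91, 0.75 or 0.51. With 10 clusters per arm,

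Var(difference in mean log risk) = [v(p0) + v(p1)]/10 × (1 − r²), where v(p) = k² + (1−p)/(mp).

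For a 40% increase (0.30 to 0.42), v(0.42) = 0.0625 + 0.58/105 = 0.0680. The unadjusted variance is (0.0718 + 0.0680)/10 = 0.0140 and the noncentrality is ln(1.4)/√0.0140 = 2.85. Power comes from the noncentral t with 18 df unadjusted, and with 17 df after one cluster-level covariate.

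| | df | Minimum detectable increase, 80% power | Power for a 40% increase |
|---|---|---|---|
| Unadjusted | 18 | 42% | 77% |
| r = 0.3 | 17 | 40% | 80% |
| r = 0.5 | 17 | 36% | 87% |
| r = 0.7 | 17 | 29% | 96% |

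**4. Cost if the covariate is useless (r = 0).** The critical t value moves from 2.101 to 2.110. Power for a 40% increase falls from 76.8% to 76.5%, about 0.3 points.

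**5. At the low end of the predicted effect.** Section 7.2 predicts increases of 45% to 60%. At 45% from a 30% baseline, unadjusted power is 84.5% on the log scale. On the risk-difference scale of step 1, with 18 df, it is 82.8%; adjustment on that scale gives 85.9%, 91.7% or 98.2% for r = 0.3, 0.5 or 0.7.

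These figures measure precision only. The documents give no basis for sizing bias from a covariate affected by the intervention, because they do not say which variables would be selected.

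**The case against.** The strongest defence is that the follow-up comparison has a proper use. Nothing in the protocol says that the follow-up respondents are the same individuals as at baseline, so stage 1 needs characteristics recorded at follow-up. Age and sex cannot be changed by the intervention. Section 5.3 withholds outcome analysis by arm until the end, and the full covariate list may properly sit in the statistical analysis plan. All of this stands. It does not rescue the rule as written, which covers every characteristic in the survey and lets observed imbalance decide.

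Three stronger readings are tempting, and the documents support none of them.

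- *That the plan throws away a strong covariate.* The second stage in section 5.8.5 could admit baseline coverage, and the unlisted constraint factors could include it. It is uncommitted, not excluded. Whether it is strong is unknown, since no correlation is given.
- *That the unadjusted t test is the stated main analysis.* Section 5.8.5 sets out unadjusted and adjusted analyses and calls neither primary.
- *That leaving out the constraint factors is an error.* No inflation of type I error is shown. Where balancing factors are prognostic, an unadjusted t test is typically conservative.

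It is also fair to say that the unadjusted analysis already exceeds 80% power at a 45% increase from 30%, so the gain is largest for effects below the predicted range.

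**Conclusion.** The point holds as a fault in a stated rule. Selecting adjustment factors by unquantified imbalance in a post-intervention survey leaves the adjusted primary result open to choice and could admit consequences of the intervention. That harm is possible under the wording; it is neither demonstrated nor sized.

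Separately, committing to baseline cluster coverage would probably improve precision at almost no cost. Under k = 0.25, m = 250, 10 clusters per arm and 30% baseline, the minimum detectable increase falls from 42% to between 40% and 29% for r from 0.3 to 0.7. The size of the gain rests entirely on that assumed correlation. It would serve the protocol's own wish, in section 7.2, for a margin against a smaller effect than expected.

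The sample size is correct and the unadjusted test is valid. This should be changed, but it does not threaten the trial's validity.

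**What to change.** Delete the follow-up-imbalance rule in section 5.8.2 as the source of adjustment factors; the descriptive comparison can stay. In section 5.8.5, name the covariates before any follow-up data are seen by arm:

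- Stage 1: age and sex.
- Stage 2: log baseline cluster coverage of recent HIV testing, with 17 df.
- Any further factor limited to baseline variables or variables the intervention cannot change, with one degree of freedom deducted for each cluster-level term.

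For ART initiations in section 5.8.4, adjust for the log pre-intervention initiation rate in every case, whether or not it is imbalanced. Report the unadjusted t test alongside. If the statistical analysis plan already fixes such a list, align the protocol wording with it.

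The cost is wording only. The data are already to be collected and the two-stage method already accommodates the change. One degree of freedom is lost, worth about 0.3 power points if baseline coverage proves uninformative.
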